8.3.1. Clinical Safety Laboratory Assessments

- Refer to Section 10.2 ([Appendix 2](#)) for the list of clinical laboratory tests to be performed and to the SoA (Section 1.2) for the timing and frequency.
- The investigator must review the laboratory report, document this review, and record any clinically relevant changes occurring during the study in the AE section of the CRF. The laboratory reports must be filed with the source documents. Clinically significant abnormal laboratory findings are those which are not associated with the underlying disease, unless judged by the investigator to be more severe than expected for the participant's condition.
- All laboratory tests with values considered clinically significantly abnormal during participation in the study or within 60 days after the last dose of study intervention should be repeated until the values return to normal or Baseline or are no longer considered significantly abnormal by the investigator or medical monitor.
- If such values do not return to normal/Baseline within a period of time judged reasonable by the investigator, the aetiology should be identified and the sponsor notified.
- All protocol-required laboratory assessments, as defined in Section 10.2 ([Appendix 2](#)), must be conducted in accordance with the laboratory manual and the SoA.
- Laboratory toxicity will be graded using the Adverse Event and Laboratory Value Severity Grading Table (Section 10.2.1). The Table is based upon publicly available Tables from the National Institute of Allergy and Infectious Disease Division of Microbiology and Infectious Diseases (www.niaid.nih.gov). Lymphopenia will be graded according to Common Terminology Criteria for Adverse Events (CTCAE) Version 4.0 ([U.S. Department of Health and Human Services](#), 2010).

8.4. Adverse Events and Serious Adverse Events

The definitions of an AE or SAE can be found in Section 10.3 ([Appendix 3](#)).

AEs will be reported by the participant (or, when appropriate, by a caregiver, surrogate, or the participant's legally authorised representative).

The investigator and any qualified designees are responsible for detecting, documenting, and reporting events that meet the definition of an AE or SAE and remain responsible for following up AEs that are serious, considered related to the study intervention or the study, or that caused the participant to discontinue the belimumab treatment (see Section 7).

8.4.1. Time Period and Frequency for Collecting AE and SAE Information

- All SAEs will be collected from the start of treatment until the follow-up visit at the time points specified in the SoA (Section 1.2). However, any SAEs assessed as related to study participation (e.g., study intervention, protocol-mandated procedures, invasive tests, or change in existing therapy) or related to a GSK product will be recorded from the time a participant consents to participate in the study.
- All AEs will be collected from the start of treatment until the follow-up visit at the time points specified in the SoA (Section 1.2).
- Medical occurrences that begin before the start of study intervention but after obtaining informed consent will be recorded on the Medical History/Current Medical Conditions section of the case report form (CRF) not the AE section.
- All SAEs will be recorded and reported to the sponsor or designee immediately and under no circumstance should this exceed 24 hours, as indicated in Section 10.3 (Appendix 3). The investigator will submit any updated SAE data to the sponsor within 24 hours of it being available. Non-serious related AEs should be reported using ADR CRF to the sponsor pharmacovigilance team ([contact]) via email within 5 calendar days.
- Investigators are not obligated to actively seek AEs or SAEs after the conclusion of the study participation. However, if the investigator learns of any SAE, including a death, at any time after a participant has been discharged from the study, and he/she considers the event to be reasonably related to the study intervention or study participation, the investigator must promptly notify the sponsor.

8.4.2. Method of Detecting AEs and SAEs

- The method of recording, evaluating, and assessing causality of AEs and SAEs and the procedures for completing and transmitting SAE reports are provided in Section 10.3 (Appendix 3).
- Care will be taken not to introduce bias when detecting AE and/or SAE. Open-ended and non-leading verbal questioning of the participant is the preferred method to inquire about AE occurrence.

8.4.3. Follow-up of AEs and SAEs

After the initial AE/SAE report, the investigator is required to proactively follow each participant at subsequent visits/contacts. All SAEs and related AE and non-serious and serious AEs of special interest (AESI) (i.e., post-injection systemic reactions and hypersensitivity reactions, infections, malignancies, and depression/suicidality/self-injury) will be followed until the event is resolved, stabilised, otherwise explained, or the participant is lost to follow-up (as defined in Section 7.3). Further information on follow-up procedures is given in Section 10.3 (Appendix 3).

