1. PROTOCOL SUMMARY

1.1. Synopsis

Protocol Title: A Multi-Center, Open-Label Study to Evaluate Safety, Efficacy and Pharmacokinetics of Belimumab Plus Standard Therapy in Chinese Paediatric Patients with Active Systemic Lupus Erythematosus (SLE)

Short Title: Open label study of belimumab plus standard therapy in Chinese paediatric patients with active SLE

Rationale: The purpose of this study is to evaluate the safety, efficacy and pharmacokinetics of belimumab (10 mg/kg) intravenous (IV) with standard therapy in Chinese paediatric patients aged 5 to 17 years with active SLE. This study is conducted to support the registration of IV belimumab in treating paediatric SLE indication in China.

Objectives and Endpoints:

Objectives	Endpoints
Primary	Primary
➤ To evaluate the safety and efficacy of belimumab IV in Chinese paediatric patients with SLE.	
Safety
 
➤ Incidence of adverse events of special interest (AESIs) through 52 weeks:
 
 • All Infections of special interest, including serious infections of special interest and opportunistic infections • Infusion related systemic reactions and anaphylactic reactions • Depression, suicidality • Malignancies 
Efficacy
 
➤ Incidence of patients with ≥ 4 points reduction from Baseline to Week 52 in SELENA SLEDAI

Secondary	Secondary
➤ To evaluate safety and tolerability of belimumab IV in Chinese paediatric patients with SLE	
➤ Incidence of AEs through 52 Weeks
 
➤ Incidence of SAEs through 52 Weeks

➤ To evaluate the efficacy of belimumab IV in Chinese paediatric patients with SLE	
➤ Incidence of patients with ≥ 4 points reduction from Baseline in SELENA SLEDAI by visit
 
➤ Change from Baseline to Week 52 in Physician Global Assessment (PGA)

Objectives	Endpoints
	
 ➤ Change from Baseline to Week 52 in Parent Global Assessment (ParentGA) ➤ Change from Baseline in daily prednisone equivalent dose at Week 52 ➤ Time to first flare/ first severe flare over 52 weeks

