Administration of belimumab may result in infusion-related systemic reactions and allergic/hypersensitivity reactions.	Administration of belimumab may result in infusion and hypersensitivity reactions, which can be severe and can be fatal. Delay in the onset of serious hypersensitivity reactions can occur. Belimumab has been associated with delayed type non-acute hypersensitivity reaction (HSR)/serum sickness, although	
Participants with a history of an anaphylactic reaction to parenteral administration of contrast agents, human or murine proteins, or monoclonal antibodies will be excluded from this study.
 
Participants will remain under clinical supervision for 3 hours after completion of the first 2 belimumab infusions.
 
Participants will be made aware of the potential risk, the signs and symptoms of such reactions, and the importance of immediately seeking medical

Potential Risk of Clinical Significance	Summary of Data/Rationale for Risk	Mitigation Strategy
	
no relationship to anti-drug antibody (ADA) has been established.
 
Infusion-related systemic reactions and hypersensitivity reactions occur more frequently with the first two doses and tend to decrease with subsequent doses.
	attention. Patients will be given an alert card for hypersensitivity/allergic reactions.
Malignancy		
As with other immunomodulating agents, the mechanism of action of belimumab may increase the potential risk for the development of malignancies.	Immunomodulatory drugs like belimumab may increase the risk of malignancy. To date, no causal relationship between belimumab and malignancy, including B cell lymphoma, has been detected.	
Participants with a history of malignancy in the 5 years prior to screening will be excluded.
 
Monitor patients for signs and symptoms of malignancy, monitor laboratory values, request that patients report signs and symptoms. Treat appropriately.

Interactions with Vaccinations		

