3. OBJECTIVES AND ENDPOINTS

Objectives	Endpoints
Primary	Primary
➤ To evaluate the safety and efficacy of belimumab IV in Chinese paediatric patients with SLE.	
Safety
 
➤ Incidence of adverse events of special interest (AESIs) through 52 weeks:
 
 • All infections of special interest, including serious infections of special interest and opportunistic infections • Infusion-related systemic reactions and anaphylactic reactions • Depression, suicidality • Malignancies 
Efficacy
 
➤ Incidence of patients with ≥ 4-point reduction from Baseline to Week 52 in SELENA SLEDAI

Objectives	Endpoints
Secondary	Secondary

 ➤ To evaluate safety and tolerability of belimumab IV in Chinese paediatric patients with SLE 	
 ➤ Incidence of AEs through 52 Weeks ➤ Incidence of SAEs through 52 weeks

 ➤ To evaluate the efficacy of belimumab IV in Chinese paediatric patients with SLE 	
 ➤ Incidence of patients with \geq4-point reduction from Baseline in SELENA SLEDAI by visit ➤ Change from Baseline to Week 52 in Physician Global Assessment (PGA) ➤ Change from Baseline to Week 52 in Parent Global Assessment (ParentGA) ➤ Change from Baseline in daily prednisone equivalent dose at Week 52 ➤ Time to first flare/ first severe flare over 52 weeks

 ➤ To evaluate the pharmacokinetics of belimumab (10 mg/kg) IV in Chinese paediatric patients with SLE 	
 ➤ Median belimumab concentration levels at Day 0, 7 and 14 days post first dose, and pre-infusion and post-infusion at Day 84 ➤ The PK will be evaluated with respect to clearance, volume of distribution and half-life, and individual steady state exposures Cmin, Cavg, Cmax and AUC.
Other CCI	Other

AESI- adverse events of special interest, AUC- Area under the concentration curve, Cmin- the minimum blood plasma concentration reached by a drug prior to administration of a second dose, Cavg- average plasma concentration, IV- Intravenous, ParentGA - Parent Global Assessment, PGA- Physician Global Assessment, SELENA SLEDAI- Safety of Estrogen in Lupus National Assessment - Systemic Lupus Erythematosus Disease Activity Index

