8.3. Safety Assessments

Planned time points for all safety assessments are provided in the SoA (Section [1.2](#)).

- A complete physical examination will be included at screening and symptoms driven physical examination at the time points mentioned in the SoA table (Section [1.2](#)).
- Adverse event (including infusion-related and hypersensitivity reactions, infections and malignancies) reported throughout the 52-week treatment period.
- Haematological and clinical chemistry parameters (including urinalysis) throughout the 52-week treatment period.
- Vital signs (i.e., heart rate and systolic and diastolic blood pressure) throughout the 52-week treatment period.
- Additional safety tests (such as vital signs, physical examinations and laboratory safety tests) or change in timing or addition of assessments may be performed during the course of the study based on newly available data to ensure appropriate safety monitoring.

- The possible suicidality related event (PSRAE) form must be completed in the eCRF, if evidence of suicidal behaviour or ideation by a participant is detected at any visit.

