Fever (oral > 12 hours)	37.7-38.5°C or 100.0-101.5°F	38.6-39.5°C OR 101.6-102.9°F	39.6-40.5°C OR 103-105°F	> 40.5°C OR > 105°F
Headache	Mild; No treatment req	Mod; or non-narcotic analgesia treatment	Severe; OR responds to initial narcotic treatment	Intractable; OR requiring repeated narcotic treatment
Allergic Reaction	Pruritus without rash	Localised urticaria	Generalised urticaria angioedema	Anaphylaxis
Cutaneous/Rash/Dermatitis	Erythema, pruritus rash OR dry desquamation	Diffuse maculopapular OR dry desquamation	Vesiculation OR moist desquamation ulceration	ANY ONE: mucous membrane involvement, suspected Stevens-Johnson (TEN), erythema multiforme, necrosis req surgery, exfoliative dermatitis
Local Reaction (secondary to parenteral treatment- not vaccination or skin test)	Erythema	Induration < 10 mm OR inflammation OR phlebitis	Induration > 10 mm OR ulceration	Necrosis of skin
Fatigue	Normal activity Reduced < 25%	Normal activity Reduced 25-50%	Normal activity reduced > 50%; cannot work	Unable to care for self

Adverse Event and Laboratory Value Severity Grade Table (continued)

NEUROLOGIC	GRADE 1 MILD	GRADE 2 MODERATE	GRADE 3 SEVERE	GRADE 4 POTENTIALLY LIFE- THREATENING
Neuro-cerebellar	Slight incoordination OR dysdiadochokinesia	Intention tremor OR dysmetria OR slurred speech OR nystagmus	Ataxia requiring assistance to walk or arm incoordination interfering with ADLs	Unable to stand
Neuro-psych/mood		none	Severe mood changes requires medical intervention	Acute psychosis requiring Hospitalisation
Paraesthesia (burning, tingling, etc.)	Mild discomfort; no treatment needed	Mod discomfort non-narcotic analgesia req	Severe discomfort; OR narcotic analgesia req with symptomatic improvement	Incapacitating; OR not responsive to narcotic analgesia
Neuro-motor	Mild weakness in muscle of feet but able to walk and/or mild increase or decrease in reflexes	Mod weakness in feet (unable to walk on heels and/or toes), mild weakness in hands, still able to do most hand tasks and/or loss of previously present reflex or development of hyperreflexia and/or unable to do deep knee bends due to weakness	Marked distal weakness (unable to dorsiflex toes or foot drop), and mod proximal weakness ie, in hands interfering with ADLs and/or requiring assistance to walk and/or unable to rise from chair unassisted	Confined to bed or wheelchair because of muscle weakness

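### Does the AESI list in Section 8.4.3, which names hypersensitivity reactions, contradict the primary safety endpoint, which names infusion-related and anaphylactic reactions?

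*Protocol*

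**What the plan says.** The primary safety endpoint is the incidence of AESIs through 52 weeks. It has four components: infections of special interest, a reaction component, depression and suicidality, and malignancies. Section 3 words the reaction component as "Infusion-related systemic reactions and anaphylactic reactions". The synopsis has "Infusion related systemic reactions and anaphylactic reactions", which differs only by a hyphen, and Section 9.4.1.1 repeats the Section 3 wording.

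Section 8.4.3 sets out which events the investigator must follow until they resolve, stabilise or are otherwise explained. It includes serious and non-serious "AEs of special interest (AESI) (i.e., post-injection systemic reactions and hypersensitivity reactions, infections, malignancies, and depression/suicidality/self-injury".

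The other places that bear on the point are:

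- Section 2.3.1 states the risk as "Administration of belimumab may result in infusion-related systemic reactions and allergic/hypersensitivity reactions" and adds "Delay in the onset of serious hypersensitivity reactions can occur. Belimumab has been associated with delayed type non-acute hypersensitivity reaction (HSR)/serum sickness".
- Section 8.3 lists, among the safety assessments, "Adverse event (including infusion-related and hypersensitivity reactions, infections and malignancies) reported throughout the 52-week treatment period".
- Section 10.2.1 grades allergic reaction in four steps. Grade 3 is "Generalised urticaria angioedema" and Grade 4 is anaphylaxis.
- Section 2.2.1, describing the paediatric study BEL114055, gives an AESI list that pairs infusion with hypersensitivity reactions.

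**The concern.** The list in Section 8.4.3 is introduced as a definition, not as examples, and it uses the same term, AESI, as the primary endpoint. Read literally, the protocol gives one term two contents. The broader one includes every hypersensitivity reaction. The narrower one names only infusion-related systemic reactions and anaphylaxis.

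The gap falls on a risk that the protocol itself describes. Section 2.3.1 warns that "Delay in the onset of serious hypersensitivity reactions can occur" and links belimumab to serum sickness. A child with delayed urticaria or serum sickness would be followed as an AESI yet might be missing from the AESI incidence. The study has one arm and no formal testing, so that incidence is the primary safety result. Two analysts reading different sections could report different primary counts.

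**Working it through.** **The lists side by side**

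| Place | Purpose | Reaction wording | Infection wording |
|---|---|---|---|
| Synopsis, Section 3, Section 9.4.1.1 | Define and analyse the primary endpoint | infusion-related systemic; anaphylactic | infections of special interest |
| Section 8.4.3 | Sets how long events are followed | post-injection systemic; hypersensitivity | infections, unqualified |
| Section 8.3 | Lists safety assessments, with examples of AEs | infusion-related; hypersensitivity | infections, unqualified |
| Section 2.3.1 | Describes known risks | infusion-related systemic; allergic/hypersensitivity | not in this row of the table |

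1. The three places that define or analyse the endpoint agree with one another. The only outlier that uses the term AESI for this trial's own procedures is the follow-up rule.
2. Section 8.4.3 departs from the endpoint list in other ways too. It drops the qualifier on infections, adds self-injury, and refers to injections in a study that gives only infusions. That pattern suggests shorthand carried over from product-level text, not a second endpoint definition. The hypotension row of Section 2.3.1 shows the same origin: it pairs infusion with post-injection reactions.
3. The two rules can both be obeyed. Following a wider set of events to resolution does not alter which events are counted in the primary endpoint.
4. What lies outside the endpoint is narrower than all hypersensitivity short of anaphylaxis. Generalised urticaria or angioedema during or soon after an infusion can be counted as an infusion-related systemic reaction. What remains is a reaction that is neither anaphylactic nor related to an infusion, mainly the delayed type.
5. The grades in Section 10.2.1 do not settle which events are AESIs. Section 8.3.1 applies that table to laboratory toxicity, and Section 10.3.3 rates AE intensity as mild, moderate or severe. Section 8.3 does not mention AESIs.

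**Figures the plan does give**

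The safety figures in Section 9.2 use n = 65 and P(at least one) = 1 − (1 − p)^65.

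- p = 7.5%: 1 − 0.925^65 = 99.4% (stated as more than 99.0%).
- p = 4%: 1 − 0.96^65 = 93.0% (stated as more than 90%).
- Exact 95% interval at 7.5% (x = 65 × 0.075 = 4.875): 2.4% to 16.8%, as stated.

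These reproduce, and none depends on which AESI list is used.

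**How far the primary count could move**

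The protocol gives no rate for the events in question, so the rates below are assumptions.

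| Assumed rate p | Expected cases, 65p | P(at least one) |
|---|---|---|
| 0.5% | 0.33 | 28% |
| 1% | 0.65 | 48% |
| 2% | 1.30 | 73% |
| 5% | 3.25 | 96% |

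Exact (Clopper-Pearson) 95% intervals for the reaction component are:

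- 0/65: 0 to 5.5%
- 1/65 (1.5%): 0.04% to 8.3%
- 3/65 (4.6%): 1.0% to 12.9%

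Starting from 0/65 supposes that no infusion-related or anaphylactic reaction occurs at all, although Section 2.3.1 treats such reactions as expected. The upper rates would suit hypersensitivity short of anaphylaxis as a whole better than the small delayed part.

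**The case for a change.** The strongest case for a change is that a defined term should have one meaning throughout a protocol. Section 8.4.3 offers its list as a definition, and Section 2.3.1 names infusion-related and hypersensitivity reactions as two things. The AESI list in Section 2.2.1 is also the broader one, whichever study it is taken to describe. A SAP can supply search terms, but it would still have to choose between the two readings. In an open-label study that choice is better made before counts accumulate.

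Part of this stands. The labels differ, no passage says that infusion-related systemic reactions include delayed ones, and the reference to injections is a slip. What does not stand is the step from there to a faulty primary endpoint. Where the endpoint is defined, the protocol speaks with one voice, so an analyst has a clear text to follow. Which MedDRA terms and time windows make up an infusion-related or anaphylactic reaction is ordinary SAP content, and the SAP is not shown here. Widening an endpoint that is stated alike in three places, in order to match one sentence about follow-up, would be a design preference and not the correction of an error.

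**Conclusion.** The wording mismatch is real and clerical, and no change to the plan follows. The primary endpoint is fixed consistently in the synopsis, Section 3 and Section 9.4.1.1. Section 8.4.3 imposes a somewhat wider follow-up duty, which does no harm to the analysis.

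The only events with unclear primary status are hypersensitivity reactions that are neither anaphylactic nor infusion-related. Section 8.4.1 has all AEs collected from the start of treatment, and Section 9.4.1.1 tabulates them by system organ class and preferred term. AE and SAE incidence are secondary endpoints. A delayed reaction would therefore be visible in the report even if left out of the AESI count. With no hypothesis test, no decision threshold hangs on one case more or less.

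Under assumed rates of 0.5% to 2%, the expected shift is 0.33 to 1.3 participants in 65. This conclusion rests on two assumptions: that analysts take the endpoint from the sections that define it, and that case identification is specified in the SAP in the usual way. Tidying the shorthand in Section 8.4.3 at some later amendment would be harmless, but nothing in the analysis depends on it.

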8.4.4. Regulatory Reporting Requirements for SAEs

- Prompt notification by the investigator to the sponsor of a SAE is essential so that legal obligations and ethical responsibilities towards the safety of participants and the safety of a study intervention under clinical investigation are met.
- The sponsor has a legal responsibility to notify both the local regulatory authority and other regulatory agencies about the safety of a study intervention under clinical investigation. The sponsor will comply with country-specific regulatory requirements relating to safety reporting to the regulatory authority, Institutional Review Boards (IRB)/Independent Ethics Committees (IEC), and investigators.
- For all studies except those utilizing medical devices, investigator safety reports must be prepared for suspected unexpected serious adverse reactions (SUSAR) according to local regulatory requirements and sponsor policy and forwarded to investigators as necessary.
- An investigator who receives an investigator safety report describing a SAE or other specific safety information e.g., summary or listing of SAEs) from the sponsor will review and then file it along with the Investigator's Brochure and will notify the IRB/IEC, if appropriate according to local requirements.

